We have investigated the mechanisms of weight loss on a HPD using a rat model of obesity induced by a Western diet (WD, 45% fat, 20% protein, 35% carbohydrate including 17% sucrose). After 12 weeks, half were switched to an isocaloric HPD (9% fat, 52% protein, 39% carbohydrate; n=11) for 6 weeks and the other half remained on the WD (n=10). Age-matched control rats (n=8) were fed a normal diet (ND, 9% fat, 29% protein, 62% carbohydrate) for the same period (18 weeks). The body fat mass of rats that remained on a WD was 77.7% higher than that of rats on a ND (Fig. 1A). Rats switched to a HPD for 6 weeks had a 29% reduction in body fat ($p<0.01$) compared to rats remaining on a WD. Rats switched from WD to HPD had equivalent caloric intake to rats maintained on a WD, indicating that reduced body fat mass is not attributable simply to reduced energy intake.

We then compared the microbiome of the WD and HPD groups. There was a highly significant difference in composition by weighted UniFrac analysis ($p<10^{-5}$) (Fig. 1B). At the genus level, the HPD microbiome was characterized by expansion of *Akkermansia*, *Ruminococcus*, and *Bacteroides* and depletion of *Lactobacillus* and *Turicibacter* (Fig. 1C). The HPD group had statistically significantly increased abundance of 114 operational taxonomic units (OTUs) selected at 97% similarity (corresponding approximately to species) after adjustment for multiple hypothesis testing (q-values). Of these, *Akkermansia muciniphila* ($q=0.008$) and an unclassified Clostridiales ($q=0.04$) had a statistically significant inverse correlation with fat mass after adjustment for diet. The correlation of *Akkermansia muciniphila* with reduced fat is consistent with findings in gastric bypass patients and studies indicating that *Akkermansia muciniphila* reduces adiposity and hyperglycemia (25, 27-29). There was decreased abundance of 188 OTUs, of which an unclassified RF39 ($q=0.0001$) and a *Phascolarctobacterium* ($q=0.02$) were correlated with fat mass. Interestingly, RF 39 is a member of the Mollicutes class, which is dramatically increased in mice on a Western diet⁽³¹⁾.

[figure not shown]

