Expected Results/Pitfalls/Significance: We do not anticipate problems in conducting the proposed human experimental studies. Our preliminary data indicate that an isocaloric high protein diet is effective at achieving a reduction in BMI in obese subjects. It is therefore likely that the results will parallel those of the preliminary studies due to the long-term study design and larger study population. It is expected that there is inhibition of the release of ghrelin, which will also be reflected through satiety questionnaires which will be performed during the study.

B. Aim 2. Characterize the changes in the fecal microbiome induced by a high protein diet.

Rationale and hypothesis: Based on our preclinical rodent model data, we hypothesize that a high protein diet will shift the composition of the microbiome of obese subjects, including increased *Akkermansia*, and that this will result in an altered metagenome (abundances of bacterial genes).

Study design: This is a randomized study using the same subjects described in Aim 1. Nutritional assessment, physical examination, bioelectrical impedance, laboratories will be performed at baseline, and weeks 2, 4, 6, 8, 12 and 16. Stool samples will be collected on day 3, 7, 14, 17, 21, 28, 42, 56, 84 and 112.

Study timeline: Data collection will be completed at week 16. The stool samples collected during the study period will be used for 16S rRNA sequencing, shotgun metagenomics, and data analysis.

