two groups. The data for all time points will then be fitted to a multivariate model under a negative binomial distribution using DESeq2 with diet group, time point, interaction between diet and time point, baseline BMI, age, sex, and smoking status as covariates. This model will be compared to a reduced model that does not include the diet:time point interaction⁽⁷⁰⁾. A likelihood ratio test will be used to identify microbes with differential abundance by diet at time points after baseline. Estimates of significance will be adjusted for multiple hypothesis testing⁽⁷¹⁾. OTUs that are differentially abundant on a HPD will be grouped by hierarchical clustering, which we anticipate will highlight distinct kinetic patterns of microbial change.

Expected results/potential pitfalls: We do not anticipate problems with the collection or transportation of fecal samples to our clinical research unit. We predict that *Akkermansia* will significantly increase on a HPD as was seen in our rodent studies. We further predict that most HPD-responsive microbes will have altered abundance within the first 3 to 7 days as has been observed in other dietary studies^(72,73). We estimate a 20% dropout rate based on our high protein meal replacement study, leaving approximately 80 subjects per group. This compares favorably to published studies reporting dietary effects on the microbiome using sample sizes of 10-15^(72,73,74). We anticipate that a HPD will have a similar magnitude of effect as these previously studied diets and hence we expect to have sufficient numbers to detect compositional differences.

2.2 Identification of metagenes affected by a high protein diet.

Experimental protocol: We will assess the functional consequences of altered microbial composition by sequencing the genes carried by intestinal microbes. Shotgun sequencing of DNA extracted from fecal samples will be performed using the HiSeq 3000 with a target depth of 10 GB data per sample, comparable to the 11.7 GB depth used by the Human Microbiome Project for stool samples⁽⁷⁵⁾. Due to the costs of sequencing at this depth, we will only sequence baseline samples and samples from day 112.

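### *Akkermansia*, the only taxon Aim 2 predicts by name to increase, has no focused test; the planned 10-df, multiplicity-adjusted screen can lose most of the power if its effect is moderate

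*Combined protocol and SAP*

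**What the plan says.** The Aim 2 hypothesis in 4. WORK PROPOSED is broad: "we hypothesize that a high protein diet will shift the composition of the microbiome of obese subjects", with a rise in *Akkermansia* given as one component and an altered metagenome as another. Under the expected results of section 2.1, *Akkermansia* is the only taxon predicted by name: it "will significantly increase on a HPD as was seen in our rodent studies". On timing, the same paragraph predicts that "most HPD-responsive microbes will have altered abundance within the first 3 to 7 days".

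The taxon-level analysis is in the experimental protocol of section 2.1. Data from all time points are "fitted to a multivariate model under a negative binomial distribution using DESeq2 with diet group, time point, interaction between diet and time point" and baseline covariates. Then "This model will be compared to a reduced model that does not include the diet:time point interaction", and "A likelihood ratio test will be used to identify microbes with differential abundance by diet at time points after baseline". Finally, "Estimates of significance will be adjusted for multiple hypothesis testing". The method and level of adjustment are not named there; the rat work in 3. WORK ACCOMPLISHED reports q-values, which suggests false discovery rate control. No separate test of *Akkermansia* is given, no subject term is listed in the model, and no effect size or power is stated for any Aim 2 test.

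**The concern.** A directional prediction about one taxon, stated in advance, needs neither a penalty for all the other taxa sequenced nor an omnibus test over ten interaction terms. As planned, whether *Akkermansia* is declared changed depends partly on how many other OTUs are tested and how many of them respond. The likelihood ratio test also ignores the predicted direction. If the shift appears in the first week and lasts, a single before-versus-after contrast holds all the information, and the other nine degrees of freedom only raise the critical value.

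The consequence reaches Aim 3, which correlates clinical endpoints only with microbes found enriched or depleted in Aim 2.1 and builds its classifiers from those associations. If *Akkermansia* misses the Aim 2.1 threshold, it drops out of both, although Aim 3 names *Akkermansia muciniphila* as its example. A null would be hard to read: it could mean no effect or a diluted test.

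**Working it through.** **Inputs from the protocol.**
- About 100 per arm and 20% dropout: 100 × (1 − 0.20) = 80 per group, which reproduces the figure in section 2.1.
- Ten stool days after the start of the diet (3, 7, 14, 17, 21, 28, 42, 56, 84, 112). Day 0 is not in that list, but the Study Visits list puts stool collection at week 0, and section 2.1 compares groups at baseline. That makes 11 levels and (11 − 1) × (2 − 1) = 10 interaction df. With only the ten listed days it would be 9 df.
- Two-sided 0.05, stated for the Aim 1 secondary analyses and taken here as the general level.

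**Assumptions, not in the protocol.** The diet effect is constant after baseline; a Gaussian approximation stands in for the negative binomial model; samples are independent, as in the listed model; adjustment is Benjamini-Hochberg at 5%; 200 to 1,000 OTUs are tested; a fraction f of 1 to 30% of them respond at the same strength.

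**Step 1, noncentrality.** For a constant post-baseline shift of d SD, the 1-df contrast and the full interaction test have the same noncentrality:

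λ = d² × (80/2) / (1 + 1/10) = 36.36 d².

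The 1-df test at 0.05 has 80% power at λ = 7.85, so d = √(7.85/36.36) = 0.46 SD.

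**Step 2, degrees of freedom alone.** Noncentral chi-square power at λ = 7.85, 10 df and alpha 0.05 is 43% (45% with 9 df). This step needs no assumption about the number of OTUs. The effect detectable with 80% power rises from 0.46 to 0.67 SD.

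**Step 3, adjustment.** The Benjamini-Hochberg p-value threshold t solves

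t = 0.05 × max(1/m, f × power(t) + (1 − f) × t).

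- m = 500, f = 30%, 10 df: t = 0.05 × (0.30 × 0.0677 + 0.70 × 0.00105) = 0.00105, and power is 6.8%.
- m = 1,000, f = 1%, 10 df: less than one discovery is expected, so t = 0.05/1,000 = 0.00005, and power is 1.2%.
- Over m = 200 to 1,000 and f = 1 to 30%: about 1 to 7% with 10 df. A 1-df test under the same adjustment would have 11 to 57%.

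**Step 4, sensitivity to effect size** (m = 500, f = 1 to 30%):

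| d (SD) | λ | 1 df, 0.05 | 10 df, 0.05 | 10 df, adjusted |
|---|---|---|---|---|
| 0.46 | 7.85 | 80% | 43% | 2–7% |
| 0.60 | 13.09 | 95% | 69% | 8–39% |
| 0.80 | 23.27 | >99% | 94% | 46–85% |
| 1.02 | 37.83 | >99% | >99% | 90–99% |
| 1.25 | 56.82 | >99% | >99% | >99% |

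**Step 5, repeated samples.** If samples within a subject have a common correlation ρ and the model allows for it, λ for both tests is multiplied by 1/(1 − ρ). The comparison between tests is unchanged, but the SD scale shifts: at ρ = 0.5 the 80% reference effect is 0.46 × √0.5 = 0.33 SD.

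**Step 6, when the contrast is the weaker test.** Suppose the effect is confined to 2, 3 or 5 of the ten post-baseline days and is large enough to give the 10-df test 80% power at 0.05. Under the same independence model, the post-baseline average contrast then has 9%, 12% or 21% power.

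**The case against.** The strongest reply is that the protocol seems to expect a large effect. Section 2.1 anticipates an effect of similar magnitude to diets studied with sample sizes of 10 to 15. If that means 80% power with 10 to 15 per group, the effect is 1.25 to 1.02 SD, and the planned test keeps at least 90% power. This stands as a limit on the size of the loss. It does not settle the point: the protocol gives no number, its argument concerns compositional differences and not one taxon, and under Aim 3 it allows that *Akkermansia* may vary greatly between people.

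Second, the adjusted figures rest on an OTU count, an adjustment level and a responding fraction that the documents do not give. If other taxa respond more strongly than *Akkermansia*, the threshold loosens: with 30% of OTUs discovered it is 0.30 × 0.05 = 0.015, and power at 0.46 SD is 25%. This also stands.

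Third, section 2.1 is a kinetic analysis, and calorie restriction begins at week 2 with stool days on either side, so a response that varies over time is plausible and the interaction test suits that question. The 3 to 7 day prediction says when change appears, not that it lasts. This is a reason to keep the interaction test, not to make it the only one.

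A reader might also infer that Aim 2 as a whole fails if *Akkermansia* misses its threshold. The documents do not support that: overall composition (UniFrac with Adonis), diversity and pathway abundance each have their own analysis, and weight loss is the trial's primary outcome.

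**Conclusion.** The gap is real: the only taxon predicted by name to increase in Aim 2 has no test of its own and is judged by an omnibus test of about 10 df, adjusted across all microbes tested. For a sustained effect near 0.46 SD at 80 per group, power falls from 80% to 43% through degrees of freedom alone, and to about 1 to 7% under the assumed false discovery rate adjustment. A reader might infer that the plan removes most of the power whatever the effect. That is not supported: the loss depends on a moderate, sustained effect and on quantities the protocol leaves unstated, and near 1 SD it is small. The point concerns a secondary aim but is worth acting on, because the remedy uses data already planned and a miss carries into Aim 3.

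**What to change.** Add to section 2.1 one prespecified test of *Akkermansia* at genus level: the interaction of diet with post-baseline average versus baseline, at two-sided 0.05, outside the OTU-wide adjustment, in a model that accounts for repeated samples per subject. Label it as the single named-taxon hypothesis within the secondary Aim 2. Keep the adjusted likelihood ratio test for all taxa, *Akkermansia* included, to describe kinetics. Name the adjustment method and level, add the baseline sample to the list of stool days, and give power for the contrast over a range of effects.

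The cost is SAP wording, one extra model and one more 0.05-level test within Aim 2; no new samples or subjects are needed. It is not free of downside: the average contrast is weak if the effect is transient or confined to a few days, which is why *Akkermansia* should also stay in the kinetic screen.

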i. Study Design: This randomized controlled study will assign approximately 200 subjects (100 each) to the following arms (Appendix 1): 1) High protein diet group based on 1 gram of protein per pound of lean body mass, and 2) Standard protein diet group as control based on 0.5 gram protein per pound of lean body mass with same calories. All participants will meet with a registered dietitian, physician or nurse practitioner to assist them with their diet efforts in all the arms. In the study, the percent energy from fat will be held constant at 30% and the differences in the diets relate only to the protein and carbohydrate contents (30% protein and 40% carbohydrate, and 15% protein and 55% carbohydrate respectively). At the initial visit patient will not be calorie restricted but will have standardization of their nutritional macronutrient intake based on their group randomization. At the 2 week visit patient will then begin a 1500 calorie restricted diet with the same macronutrient composition (ie. 30% protein and 40% carbohydrate, and 15% protein and 55% carbohydrate respectively for the high and standard protein groups).

ii. Number of Subjects: Approximately 200 healthy volunteers age 30 years and older with a BMI between 27 to 40 kg/m² will be able to take part in this study.

iii. Estimated Study Duration: Accrual period is 3-4 years; anticipated dropout rate is 20%; and total study duration is approximately 5 years (taking into account data analysis).

iv. Subject Eligibility: Subjects will be assigned an enrollment number after signing the informed consent form. The subjects will complete all the screening tests and procedures as listed. When a subject completes the screening tests and procedures, the subjects will be assigned a randomization number. Subjects will be randomized into one of the two diet groups as described in Appendix 1.

The practitioner at screening will obtain each subject's date of birth, sex, race, medical history, current medications, and smoking and alcohol history. The physician will perform complete physical examinations. Height will be measured using a standardized stadiometer, while the subject stands

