Shotgun reads will be inputted into HUMAnN2 for annotation of gene families and identification of the microbial source of these genes⁽⁷⁶⁾. Individual genes will be aggregated into functional pathways using the MetaCyc database⁽⁷⁷⁾. Gene and pathway abundance for the HPD and NPD groups at baseline will be compared to confirm that randomization prevented skewing of the functional profiles of the two groups. Pathway abundance will be fitted to a multivariate model using DESeq2 with diet group/time point, baseline BMI, age, sex, and smoking status as covariates to identify functional pathways impacted by a high protein diet after adjusting for covariates. Genes belonging to HPD-associated pathways, stratified by the genus of their microbial source, will then be individually evaluated using DESeq2. This approach will reduce the number of statistical tests which might be overwhelming given the greater than 5 million genes within the intestinal metagenome⁽⁷⁵⁾. HPD-associated genes will be visualized in pathway maps to highlight the specific metabolic shifts in the microbiome at the DNA level that occur on a HPD.

Expected results/potential pitfalls: We predict that a HPD will reduce the abundance of genes in phosphotransferase pathways involved in bacterial carbohydrate metabolism, which are elevated in obese humans⁽²⁴⁾. Our estimated final sample size of 80 subjects per group would be much larger than existing metagenomics studies of obese patients which have used 6-7 subjects per group at lower sequence depths (3 GB per sample in the most recent study)^(24,26). We anticipate that the magnitude of effect of a high protein diet will be less than that in those comparisons (obese vs. lean, gastric surgery vs. non-surgically managed) but that the 10 fold larger sample size will provide sufficient power to detect metagenomic shifts.

C. Aim 3. Identify fecal microbial predictors of response to a high protein diet.

Rationale and hypothesis: The second aim of this proposal focuses on the relationship of the microbiome to clinical endpoints including weight loss, body fat loss, lipids, and

hyperglycemia. We hypothesize that subjects will vary in the responsiveness of their microbiota to a HPD based on baseline or post-dietary intervention levels of microbes such as *Akkermansia muciniphila* that respond to the HPD. The impact of these microbial changes on diet-induced weight gain will be assessed in humanized gnotobiotic mice.

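### The Aim 2.2 metagenome model names no diet-by-time test and does not link each subject's baseline and day-112 samples

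*Combined protocol and SAP*

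**What the plan says.** Section 4.B, 2.2 (Identification of metagenes affected by a high protein diet) restricts shotgun sequencing on cost grounds: "we will only sequence baseline samples and samples from day 112". The analysis sentence is "Pathway abundance will be fitted to a multivariate model using DESeq2 with diet group/time point, baseline BMI, age, sex, and smoking status as covariates", and its purpose is "to identify functional pathways impacted by a high protein diet after adjusting for covariates". Genes in the pathways found this way are then tested one by one, and section 4.C (Aim 3) applies its correlation and classifier pipeline to the same shotgun data.

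Section 2.1, on 16S abundance, is more explicit. It lists "diet group, time point, interaction between diet and time point, baseline BMI, age, sex, and smoking status as covariates" and gives the test: "This model will be compared to a reduced model that does not include the diet:time point interaction". Neither section lists a subject term or the subject's own baseline abundance as a covariate. Section 2.2 does not say that it inherits the 2.1 test.

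Under Study Design in section 4.A, both arms start the same 1500-calorie diet at the week-2 visit.

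**The concern.** With two time points in a randomized comparison, the effect of the high protein diet (HPD) relative to the normal protein diet (NPD) is the difference between arms at day 112, or equivalently the difference between arms in change from baseline. The coefficient tested decides whether the analysis answers that question, and section 2.2 does not identify it.

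The slash allows at least two models. In an additive model, the diet coefficient mixes baseline, where no diet effect is expected, with day 112. In a combined four-level factor, the right contrast exists but so does a misleading one: HPD day 112 against HPD baseline includes the calorie restriction common to both arms.

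The missing pairing is a separate gap. Two samples from one person are correlated, and the listed covariates do not account for that.

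The pathway result decides which genes are examined at all, so a pathway missed at this step is not recovered later. Section 2.2 also expects a smaller effect than earlier metagenomic comparisons and relies on sample size for power, so an inefficient test weakens the plan's own argument.

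**Working it through.** **Inputs from the plan.** "This randomized controlled study will assign approximately 200 subjects (100 each) to the following arms"; "We estimate a 20% dropout rate based on our high protein meal replacement study, leaving approximately 80 subjects per group". Check: 100 × (1 − 0.20) = 80 per group, which agrees. The documents give no power, effect size, variance or within-subject correlation for Aim 2.2.

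**Assumptions.** Log-scale normal approximation; common variance σ²; n per arm; within-subject correlation ρ from 0.3 to 0.7; one two-sided test at 0.05; baseline taken before the assigned diet begins. The day-112 effect δ is set to give 80% power on day-112 samples alone: δ/√(2σ²/n) = 1.96 + 0.84 = 2.80, so δ√n/σ = 2.80 × √2 = 3.96.

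**1. What the additive diet coefficient estimates.** It equals δ × w₁₁₂/(w₀ + w₁₁₂), where w is half the per-arm number at each time.
- 80 and 80 per arm: 40/80 = 0.50 of δ.
- 100 and 80 per arm: 40/90 = 0.44 of δ.

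A negative binomial simulation (400 runs, subject heterogeneity, true log effect 0.69) gave 0.34 and 0.31. The interaction coefficient gave 0.68 and 0.71.

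**2. What a combined factor allows.** The four diet/time cells span the same model space as diet + time + interaction (joint rank 4). Difference in change and the day-112 between-arm contrast both return δ. The within-HPD contrast returns δ plus the shared time effect: with an assumed shared effect of 0.40 it gave 1.08 to 1.10 when δ = 0.69, and 0.40 when δ = 0. With δ = 0, a shared shift of 0.3 SD and n = 80, a paired within-arm test rejects with probability Φ(0.3/√(2(1−ρ)/80) − 1.96), which is 62% at ρ = 0.3 and 93% at ρ = 0.7.

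**3. Power for the same δ.**

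| Test | Variance | ρ = 0.3 | ρ = 0.5 | ρ = 0.7 |
|---|---|---|---|---|
| Additive diet term, samples treated as independent | σ²/n assumed, σ²(1+ρ)/n true | 51% | 51% | 51% |
| Additive diet term, correct standard error | σ²(1+ρ)/n | 41% | 37% | 33% |
| Interaction, samples treated as independent | 4σ²/n assumed, 4σ²(1−ρ)/n true | 51% | 51% | 52% |
| Interaction, paired | 4σ²(1−ρ)/n | 66% | 80% | 95% |
| Day 112 only | 2σ²/n | 80% | 80% | 80% |
| Day 112, baseline-adjusted | 2σ²(1−ρ²)/n | 84% | 90% | 98% |

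Examples: the unpaired interaction has z = 3.96/2 = 1.98, and Φ((1.98 − 1.96)/√0.7) = 51%. The baseline-adjusted test at ρ = 0.3 has Φ(2.80/√0.91 − 1.96) = 84%.

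**4. Type I error without pairing.** For the additive term it is 2Φ(−1.96/√(1+ρ)): 8.6% at ρ = 0.3 and 13.3% at ρ = 0.7. For the interaction it is 2Φ(−1.96/√(1−ρ)): 1.9% and 0.03%, so that test is over-conservative.

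**The case against.** A reader might infer that the planned analysis halves the diet effect. The documents do not establish this. Section 2.1 separates its terms with commas, and section 2.2 uses commas for its other covariates but a slash here. That fits a single combined factor, which already contains the interaction. The halving needs an additive model that the plan never states, and it is exact only with equal numbers at the two times.

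A reader might also infer that the plan credits calorie restriction to protein. No section proposes a within-arm contrast. The surrounding text points to a comparison between arms: the 2.1 heading sets the high protein diet against an isocaloric normal protein diet, section 2.2 compares the two groups at baseline to check randomization, and its sample-size argument is per group.

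Nor does the plan lose most of its power: the unpaired tests fall from 80% to about 51%. Copying the 2.1 interaction into 2.2 without pairing would remove the dilution but leave power at about 51%.

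These points stand, and they limit the claim to an undefined test and missing pairing. They do not make the gap harmless. No section names the contrast, and the listed model contains nothing that links a subject's two samples. One choice escapes the standard-error problem: a day-112 between-arm contrast uses different subjects. That contrast is not named either, and it leaves the baseline sample unused.

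Aim 2.2 is secondary and mechanistic, and the metagene step of Aim 3 also requires association with clinical response and uses cross-validation. The downstream harm is therefore indirect.

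**Conclusion.** The concern holds as an underspecified test and an unpaired model, not as a demonstrated bias. The dilution (0.50 or 0.44 of the effect) and the mixing with calorie restriction are each conditional on a reading or contrast that the plan leaves open.

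The lack of pairing is common to every reading. Any test that draws on both samples then has the wrong standard error: too small for the additive diet term (type I error about 9 to 13%), too large for the interaction. A baseline-adjusted day-112 comparison would raise power from about 51% for either unpaired test to 84 to 98%, using data the plan already intends to generate.

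These figures rest on an assumed correlation of 0.3 to 0.7, an effect scaled to 80% power on day 112, a normal approximation, and a single test at nominal 0.05. Screening many pathways with multiplicity adjustment would change the absolute powers. The primary weight endpoint is unaffected.

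**What to change.** Replace the slashed term in section 2.2 with an explicit model and one named test. Two forms would serve:

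- **Baseline-adjusted comparison.** HPD minus NPD at day 112, adjusted for the subject's own baseline abundance of that pathway plus the covariates already listed. This is the more powerful form at every correlation examined.
- **Paired interaction.** Diet by time (baseline, day 112) with subject pairing, for example subject effects nested within arm. Subject effects absorb the between-subject covariates (BMI, age, sex, smoking). This form is less powerful than day 112 alone when ρ is below 0.5.

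State that a pathway is called HPD-associated only on that test, and that no within-arm change is used for this purpose.

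The cost is a small change of model specification, and possibly of software, because the baseline covariate differs from pathway to pathway. No extra samples or sequencing are needed, and the change can be made before the shotgun data are analysed.
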